10.2 Treatment Discontinuation Visit

Patients who discontinue from treatment will be asked to return to the clinic no more than 30 days after the last treatment for a treatment discontinuation visit. The visit at which a response assessment shows progressive disease may be used as the treatment discontinuation visit.

10.3 Follow-Up Assessments

Patients who discontinue early from treatment or who complete the study treatment period will be followed as outlined below. If disease progression is clinically suspected, this should be confirmed by radiological examination as soon as possible. For patients who are being treated beyond progression, see Appendix 4 for the frequency of imaging assessments to monitor response.

10.4 Post-Treatment Evaluations

Patients who discontinue study treatment for reasons other than PD (e.g., toxicity) should continue to undergo the full tumor assessment 6–8 weeks after study treatment is discontinued and

every six months thereafter until the patient dies, experiences PD, withdraws consent, or until the study closes, whichever occurs first. Patients who start a new anticancer therapy in the absence of PD should continue to be followed for progression according to the protocol schedule unless consent is withdrawn, the patient dies, or the study closes, whichever occurs first.

For patients who experience PD or who discontinue the study treatment due to an AE or SAE, full tumor assessment should be obtained within 30 days after the last dose of study treatment or before another anticancer therapy is initiated. Additional required tests for these patients are outlined in Appendix 1.

Patients that drop out prior to evaluation due to PD, AE, SAE will be assessed for survival and toxicity every 3 months until the start of new anti-lymphoma therapy.

Female patients of reproductive potential who are not surgically sterile must practice adequate birth control for a minimum of twelve months post-treatment; male patients who are not surgically sterile must practice adequate birth control for a minimum of three months post-treatment.

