10.5 Survival and Subsequent Anticancer Therapy

Survival follow-up information will be collected via telephone calls, patient medical records, and/or clinic visits approximately every 3 months until death, loss to follow-up, or study termination by the funding source of Principal Investigator. All patients who have discontinued treatment without disease progression will undergo all follow-up exams noted in Appendix 1 during follow-up. All other patients will be followed for survival and new anticancer therapy information only, unless the patient requests to be withdrawn from follow-up (this request must be documented in the source documents and signed by the investigator). If the patient withdraws from study treatment but not from follow-up, the study staff may use a public information source (e.g., county records) to obtain information about survival status only.

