14.3 Primary Efficacy Variables

Objective response is defined as a CR or PR, as determined by investigator assessment using *the Lugano Classification on Treatment Response Assessment Timepoints* (Appendix 4). Patients not meeting these criteria, including patients without any post-baseline tumor assessment, will be considered nonresponders in the analysis of objective response.

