14.4 Secondary Efficacy Variables

PFS is defined as the time from the first day of study treatment to PD or death, whichever occurs first. If a patient is alive and has not experienced PD, PFS will be independently censored at the day of the last tumor assessment. Patients with no post-baseline tumor assessments will be included in the PFS analysis but censored at the start of treatment.

OS is defined as the time from the first day of study treatment to death from any cause. For OS, patients without a date of death will be independently censored on the date a patient was last known to be alive.

Incidence of toxicity and adverse events will be summarized by frequencies and percentages for each of the two cohorts.

Patients with early withdrawal from the study will be considered as independently censored according to previous paragraphs. However, the censoring may be related to the disease status and therefore not independent. Therefore, sensitivity analyses will be conducted where these patients will be counted as events.

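### Sections 10.4 and 10.5 set different ends to survival follow-up for patients who drop out before evaluation because of PD, AE or SAE, which leaves overall survival open to informative censoring.

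*Combined protocol and SAP*

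**What the plan says.** The third paragraph of 10.4 covers one group, "Patients that drop out prior to evaluation due to PD, AE, SAE", and says that they "will be assessed for survival and toxicity every 3 months until the start of new anti-lymphoma therapy". One stopping point serves both survival and toxicity.

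Section 10.5, the dedicated survival section, collects survival information "approximately every 3 months until death, loss to follow-up, or study termination by the funding source of Principal Investigator". It then divides patients in two. For the first group, "All patients who have discontinued treatment without disease progression will undergo all follow-up exams noted in Appendix 1 during follow-up". For the rest, "All other patients will be followed for survival and new anticancer therapy information only".

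Section 2.2 makes overall survival a secondary objective in each arm. Section 14.4 defines it from the first day of study treatment to death from any cause, and says that "patients without a date of death will be independently censored on the date a patient was last known to be alive". Section 14.4 also plans a sensitivity analysis that counts early withdrawals from the study as events. Section 14.5 applies that analysis to withdrawals from intervention for reasons other than progression or death.

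**The concern.** The two sections overlap on the same patients and disagree about when survival contact ends. The 10.4 sentence is the more specific of the two, so a site could reasonably treat it as governing.

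The group need not be small. Appendix 5 places the first on-treatment response assessment at C5D1, which is 4 × 21 = 84 days, or 12 weeks, after the first dose. If that is the evaluation meant, everyone who leaves for PD or toxicity in the first 12 weeks is covered. Section 10.6 expects the last visit 2 years after the last enrolment. A patient who starts new therapy at month 3 would therefore lose 24 − 3 = 21 of the first 24 months of survival follow-up.

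These patients have left for progression or toxicity and have gone on to need further treatment. It is a reasonable inference, though not stated in the documents, that their later survival differs from that of the patients who remain. If it does, censoring them at new therapy is informative.

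**Working it through.** **Setting the rules side by side.** Take a treated patient who leaves for PD before the first response assessment and then starts new therapy.

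- Under 10.4, third paragraph, survival assessment ends when the new therapy starts.
- Under 10.5, the patient is followed about every 3 months for survival and for new anticancer therapy, until death, loss to follow-up or study termination. Recording new therapy presupposes contact after it begins.

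No reading satisfies both for deaths that follow new therapy.

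**The plan's own figures.** No event count, sample size or power is stated for overall survival, so there is no survival figure to reproduce. The response-rate design in 14.1 (25 per arm, 9 or more responders, 20% against 43%) reproduces by exact binomial calculation: type 1 error 0.0468 and power 0.818, within the stated 0.05 and 0.2 error rates. This point does not touch it.

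**Size of the effect, on assumptions.** From the documents: n = 25 per arm (14.1) and the Kaplan-Meier method (14.5). Assumed, because the documents give no values: k = 2, 4 or 8 early dropouts; all start new therapy at month 3; survival is exponential; 24-month survival is 90% in the others and S_d = 50% or 70% in dropouts.

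Expected 24-month survival with full follow-up (10.5):

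(k/25) × S_d + (1 − k/25) × 0.90

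Expected estimate with censoring at month 3 (10.4), where 3/24 = 1/8:

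[(k/25) × S_d^(1/8) + (1 − k/25) × 0.90^(1/8)] × 0.90^(7/8)

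Worked for k = 4 and S_d = 50%:

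- Full follow-up: 0.16 × 0.50 + 0.84 × 0.90 = 0.836.
- Censored: (0.16 × 0.9170 + 0.84 × 0.9869) × 0.9119 = 0.9757 × 0.9119 = 0.890.
- Difference: 5.4 points.

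A simulation of 4,000 trials per scenario, n = 25, agrees with these formulas to within about 0.2 points. Its mean 24-month estimates are:

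| Dropouts | Dropout survival | Full follow-up | Censored at new therapy | Difference | Dropouts counted as events |
|---|---|---|---|---|---|
| 2 | 70% | 88.3% | 89.7% | 1.4 | 82.7% |
| 2 | 50% | 86.7% | 89.5% | 2.8 | 82.8% |
| 4 | 70% | 86.7% | 89.5% | 2.8 | 75.5% |
| 4 | 50% | 83.6% | 89.0% | 5.4 | 75.6% |
| 8 | 70% | 83.5% | 89.1% | 5.6 | 61.2% |
| 8 | 50% | 77.0% | 87.8% | 10.8 | 61.1% |

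When dropouts survive as well as the others (90%), the first two estimates agree apart from simulation noise (for 4 dropouts, 90.0% and 89.9%).

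**What the sensitivity analysis recovers.** The last column applies the event-counting rule to every dropout. It falls well below full follow-up in each row (75.6% against 83.6% in the worked case). It bounds the answer from below and does not replace the missing deaths.

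**The case against.** The strongest reply is that 10.5 is the survival section, that it plainly expects contact after new therapy, and that the cut-off in 10.4 reads naturally as a limit on toxicity follow-up. Sections 11.1.1 and 16.2.1 also end adverse-event recording or safety follow-up at subsequent anticancer therapy. On that view, bias arises only if staff follow one sentence over a whole section. This is fair, and it is why the point is a conflict to reconcile rather than a settled loss of data. It does not remove the conflict, because the 10.4 sentence names survival expressly.

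The safeguards are also real. Section 10.5 allows telephone calls, medical records and, for patients off treatment but still in follow-up, public records. Section 14.5 brings patients who stop for toxicity without progression into the sensitivity analysis. Patients who leave for PD are not clearly covered by it.

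Precision matters too. At 83.6% survival with 25 patients, the binomial standard error is √(0.836 × 0.164 / 25) = 0.074, or about 7 points, so most of the biases shown are smaller than one standard error. No decision in 14.1 rests on survival. That limits the consequence, but a bias is not excused by a wide interval, and deaths not collected may not be recoverable later.

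A reader might infer three stronger points that the documents do not support:

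- **That 10.4 cancels tumor assessment for these patients.** The sentence is silent on scans. The first paragraph of 10.4 keeps assessments after stops other than PD, the second requires one after a PD, AE or SAE stop, and 10.5 keeps the Appendix 1 exams for patients without progression.
- **That these patients drop out of the survival analysis.** They stay in it, censored when last known alive. Only later deaths are at risk.
- **That the response rate is shifted.** This would need a lost scan, which the text does not establish. Section 14.3 already fixes the handling: patients not meeting response criteria, "including patients without any post-baseline tumor assessment, will be considered nonresponders".

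**Conclusion.** The conflict stands. Sections 10.4 and 10.5 give incompatible ends of survival follow-up for the same early dropouts, and the 10.4 rule does not fit an endpoint defined as death from any cause. If 10.4 is followed, the independence assumed in 14.4 is doubtful and Kaplan-Meier survival is likely to be too high. The range of about 1 to 11 points at 24 months is an illustration. It depends on the assumed number of dropouts, their survival, the survival of the others and new therapy at month 3, none of which the documents supply. The effect disappears if sites follow 10.5, or if dropouts survive as well as the others. This is an inconsistency in wording that affects a secondary endpoint. The primary response analysis and its error rates are unaffected.

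**What to change.** In the third paragraph of 10.4, separate survival from toxicity. State that survival status and new anticancer therapy are collected about every 3 months for all treated patients, including those who drop out before evaluation, until death, loss to follow-up or study termination as in 10.5, and that starting new therapy does not end survival follow-up.

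Do not simply delete the new-therapy phrase, because that would leave 3-monthly toxicity assessment without an end. The end of toxicity follow-up should be reconciled separately with 11.1.1 and 16.2.1.

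Add a sentence saying that the third paragraph does not replace the tumor assessments that the first two paragraphs of 10.4 and section 10.5 already require for AE or SAE dropouts without PD.

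The cost is a wording amendment and a few more calls or record checks, of a kind already planned under 10.5. Sample size, type 1 error and power do not change.

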10.5 Survival and Subsequent Anticancer Therapy

Survival follow-up information will be collected via telephone calls, patient medical records, and/or clinic visits approximately every 3 months until death, loss to follow-up, or study termination by the funding source of Principal Investigator. All patients who have discontinued treatment without disease progression will undergo all follow-up exams noted in Appendix 1 during follow-up. All other patients will be followed for survival and new anticancer therapy information only, unless the patient requests to be withdrawn from follow-up (this request must be documented in the source documents and signed by the investigator). If the patient withdraws from study treatment but not from follow-up, the study staff may use a public information source (e.g., county records) to obtain information about survival status only.

10.6 End of Study

The end of this study is defined as the date when the last patient, last visit (LPLV) occurs or the date at which the last data point required for statistical analysis (i.e., efficacy analysis) or safety follow-up is received from the last patient, whichever occurs later. LPLV is expected to occur 2 years after the last patient is enrolled.

11.0 TOXICITIES/SIDE EFFECTS

11.1 Definition of Adverse Event

An AE is any unfavorable and unintended sign, symptom, or disease temporally associated with the use of an investigational medicinal product (IMP) or other protocol-imposed intervention, regardless of attribution.

This includes the following:

AEs not previously observed in the patient that emerge during the protocol-specified AE reporting period, including signs or symptoms that were not present prior to the AE reporting period

Complications that occur as a result of protocol-mandated interventions (e.g., invasive procedures such as cardiac catheterizations)

If applicable, AEs that occur prior to assignment of study treatment associated with medication washout, no treatment run-in, or other protocol-mandated intervention

Pre-existing medical conditions (other than the condition being studied) judged by the investigator to have worsened in severity or frequency or changed in character during the protocol-specified AE reporting period.

An adverse event is considered serious if it:

Results in death

Is life-threatening

Results in inpatient hospitalization of over 24 hours or prolongation of existing hospitalization

Results in persistent or significant incapacity or substantial disruption of the ability to conduct normal life functions

Results in a congenital anomaly/birth defect

Is an Important Medical Event (IME) that may not result in death, be life threatening, or require hospitalization may be considered serious when, based upon medical judgment, they may jeopardize the patient or participant and may require medical or surgical intervention to prevent one of the outcomes listed in this definition

Hospital admission for a planned procedure/disease treatment is not considered an SAE.

11.1.1 Adverse Events

All AEs (including SAEs and protocol-defined events of special interest [see Section 6.2]), regardless of attribution, will be recorded until 30 days after the last dose of study treatment, until study discontinuation/termination, or until initiation of subsequent anticancer therapy, whichever occurs first. After this period, investigators should report only those AEs (including pregnancy-related AEs) considered related to prior study treatment. Ongoing AEs considered related to study treatment will be followed until one of the following conditions is met: the event has resolved to baseline grade, the event is assessed by the investigator as stable, new anticancer treatment is initiated, the patient is lost to follow-up, the patient withdraws consent, or it has been determined that study treatment or participation is not the cause of the AE.

See the Schedule of Assessments provided in Appendix 1 for specified follow-up assessments.

11.1.2 Assessment of Adverse Events

All AEs and SAEs, whether volunteered by the patient, discovered by study personnel during questioning, or detected through physical examination, laboratory test, or other means, will be reported appropriately. Each reported AE or SAE will be described by its duration (i.e., start and end dates), regulatory seriousness criteria if applicable, suspected relationship to the study drug (see following guidance), and actions taken.

To ensure consistency of AE and SAE causality assessments, investigators should apply the following general guideline:

Yes

There is a plausible temporal relationship between the onset of the AE and administration of MDPL3280A, and the AE cannot be readily explained by the patient's clinical state, intercurrent illness, or concomitant therapies; and/or the AE follows a known pattern of response to MDPL3280A; and/or the AE abates or resolves upon discontinuation of MDPL3280A or dose reduction and, if applicable, reappears upon re-challenge.

No

Evidence exists that the AE has an etiology other than MDPL3280A (e.g., pre-existing medical condition, underlying disease, intercurrent illness, or concomitant medication); and/or the AE has no plausible temporal relationship to ATEZOLIZUMAB administration (e.g., cancer diagnosed 2 days after first dose of study drug).

Expected AEs are those AEs that are listed or characterized in the Package Insert (PI) or current Investigator's Brochure.

Unexpected AEs are those not listed in the PI or current Investigator's Brochure or not identified. This includes AEs for which the specificity or severity is not consistent with the description in the PI or Investigator's Brochure. For example, under this definition, hepatic necrosis would be unexpected if the PI or Investigator's Brochure only referred to elevated hepatic enzymes or hepatitis.

11.1.3 Adverse Events of Special Interest

Adverse events of special interest (AESIs) are defined as a potential safety problem, identified as a result of safety monitoring of the IMP. AESIs are a subset of Events to Monitor (EtMs) of scientific and medical concern specific to the product, for which ongoing monitoring and rapid communication by the Investigator to the Sponsor is required. Such an event might require further investigation in order to characterize and understand it. Depending on the nature of the event, rapid communication by the trial Sponsor to other parties (e.g., Regulatory Authorities) may also be warranted.

The following AEs are considered of special interest and must be reported to the Genentech Drug Safety expeditiously (see Section 17.2 for reporting instructions), irrespective of regulatory seriousness criteria:

Adverse events of special interest for this study include the following:

Cases of potential drug-induced liver injury that include an elevated ALT or AST in combination with either an elevated bilirubin or clinical jaundice, as defined by Hy's law:

Treatment-emergent ALT or AST > 3xULN in combination with total bilirubin > 2xULN

Treatment-emergent ALT or AST > 3xULN in combination with clinical jaundice

- Data related to a suspected transmission of an infectious agent by the study drug (STIAMP), as defined below:
 - Any organism, virus, or infectious particle (e.g., prion protein transmitting transmissible spongiform encephalopathy), pathogenic or non-pathogenic, is considered an infectious agent. A transmission of an infectious agent may be suspected from clinical symptoms or laboratory findings that indicate an infection in a patient exposed to a medicinal product. This term applies only when a contamination of the study drug is suspected

Pneumonitis

Colitis

Endocrinopathies: Diabetes mellitus, pancreatitis, adrenal insufficiency, hyperthyroidism, and hypophysitis

Hepatitis, including AST or ALT > 10xULN

Systemic lupus erythematus (SLE)

Guillain-Barré syndrome

Myasthenia gravis or myasthenic syndrome

Meningoencephalitis

Nephritis

Myositis

Ocular toxicities (e.g., uveitis, retinitis, optic neuritis)

Myopathies, including rhabdomyolysis

Grade >/=2 cardiac disorders (e.g., atrial fibrillation, myocarditis, pericarditis)

Vasculitis

Autoimmune hemolytic anemia

Severe cutaneous reactions (e.g. Stevens-Johnson Syndrome, dermatitis bullous, toxic epidermal necrolysis)

Events suggestive of hypersensitivity, cytokine release, influenza like illness, systemic inflammatory response syndrome, SIA(systemic immune activation) or infusion reaction syndromes

11.1.4 Post- Study Adverse Events

The investigator should expeditiously report any SAE occurring after a patient has completed or discontinued study participation if attributed to prior ATEZOLIZUMAB exposure. If the investigator should become aware of the development of cancer or a congenital anomaly in a subsequently

conceived offspring of a female patient who participated in the study, this should be reported as an SAE. adequately to Genentech Drug Safety during the follow-up period.

11.1.5 Specific Instructions for Recording Adverse Events

Investigators should use correct medical terminology/concepts when reporting AEs or SAEs. Avoid colloquialisms and abbreviations. For more information, refer to Section 17.2.

Eliciting Adverse Events

A consistent methodology for eliciting AEs at all subject evaluation time points should be adopted. Examples of non-directive questions include:

“How have you felt since your last clinical visit?”

“Have you had any new or changed health problems since you were last here?”

Specific Instructions for Recording Adverse Events

Investigators should use correct medical terminology/concepts when reporting AEs or SAEs. Avoid colloquialisms and abbreviations. (See Section 11.3-11.7)

Exchange OF SINGLE CASE REPORTS

Memorial Sloan Kettering (MSK) will be responsible for collecting all protocol-defined Adverse Events (AEs) and Special Situation Reports (including pregnancy reports) originating from the Study for the Product.

Investigators must report all Adverse Events/Serious Adverse events (SAEs), AEs of Special Interest (AESIs) and Special Situation Reports (including pregnancy reports) adequately to Genentech within the timelines described below. The completed MedWatch or CIOMS I form or Genentech approved reporting forms should be faxed immediately upon completion to Genentech Drug Safety at:

[contact]

Email: [contact]

Relevant follow-up information should be submitted to Genentech Drug Safety as soon as it becomes available and/or upon request.

MEDWATCH 3500A REPORTING GUIDELINES

In addition to completing appropriate patient demographic and suspect medication information, the report should include the following information within the Event Description (section 5) of the MedWatch 3500A form:

Protocol description (and number, if assigned)

Description of event, severity, treatment, and outcome if known

Supportive laboratory results and diagnostics

Investigator's assessment of the relationship of the adverse event to each investigational product and suspect medication

Follow-Up Information

Additional information may be added to a previously submitted report by any of the following methods:

Adding to the original MedWatch 3500A report and submitting it as follow-up

Adding supplemental summary information and submitting it as follow-up with the original MedWatch 3500A form

Summarizing new information and faxing it with a cover letter including patient identifiers (i.e. D.O.B. initial, patient number), protocol description and number, if assigned, brief adverse event description, and notation that additional or follow-up information is being submitted (The patient identifiers are important so that the new information is added to the correct initial report)

MedWatch 3500A (Mandatory Reporting) form is available at

<http://www.fda.gov/downloads/AboutFDA/ReportsManualsFo rms/Forms/UCM048334.pdf>

Reporting to Regulatory Authorities, Ethics Committees and Investigators

MSK, as the Sponsor of the Study, will be responsible for the expedited reporting of safety reports originating from the Study to the Regulatory Authorities (FDA) where it has filed a clinical trial approval, in compliance with local regulations.

Sponsor will be responsible for the distribution of safety information to its own investigators, where relevant

Additional Reporting Requirements for IND Holders (if applicable):

For Investigator-Initiated IND Studies, some additional reporting requirements for the FDA apply in accordance with the guidance set forth in 21 CFR §600.80.

Events meeting the following criteria need to be submitted to the Food and Drug Administration (FDA) as expedited IND Safety Reports according to the following guidance and timelines:

7 Calendar Day Telephone or Fax Report:

The Investigator is required to notify the FDA of any fatal or life-threatening adverse event that is unexpected and assessed by the Investigator to be possibly related to the use of atezolizumab. An unexpected adverse event is one that is not already described in the atezolizumab Investigator Brochure. Such reports are to be telephoned or faxed to the FDA and Genentech/Roche within 7 calendar days of first learning of the event.

15 Calendar Day Written Report

The Investigator is also required to notify the FDA and all participating investigators, in a written IND Safety Report, of any serious, unexpected AE that is considered reasonably or possibly related to the use of atezolizumab. An unexpected adverse event is one that is not already described in the atezolizumab investigator brochure.

Written IND Safety reports should include an Analysis of Similar Events in accordance with regulation 21 CFR

§ 312.32. All safety reports previously filed by the investigator with the IND concerning similar events should be analyzed and the significance of the new report in light of the previous, similar reports commented on.

Written IND safety reports with Analysis of Similar Events are to be submitted to the FDA, Genentech/Roche, and all participating investigators within 15 calendar days of first learning of the event. The FDA prefers these reports on a MedWatch 3500 form, but alternative formats are acceptable (e.g., summary letter).

FDA fax number for IND Safety Reports:

Fax: [name]

All written IND Safety Reports submitted to the FDA by the Investigator must also be faxed to Genentech/Roche Drug Safety:

[contact] or [contact]

And Sponsor will be responsible for the distribution of safety information to Site IRB

[contact]

[contact]

For questions related to safety reporting, please contact Genentech/Roche Drug Safety:

[contact]

[contact] or [contact]

AGGREGATE REPORTS

IND ANNUAL REPORTS

All IND annual reports submitted to the FDA by the Sponsor-Investigator should be copied to Genentech

Copies of such reports should be emailed to Genentech at: Genentech Drug Safety CTV mail box: [contact]

Sponsor will forward a copy of the Final Study Report to Genentech/Roche upon completion of the Study.

QUERIES

Queries related to the Study will be answered by *Sponsor*. However, responses to all safety queries from regulatory authorities or for publications will be discussed and coordinated between the Parties. The Parties agree that Genentech/Roche shall have the final say and control over safety queries relating to the Product. *Sponsor* agrees that it shall not answer such queries from regulatory authorities and other sources relating to the Product independently but shall redirect such queries to Genentech/Roche.

Both Parties will use all reasonable effort to ensure that deadlines for responses to urgent requests for information or review of data are met. The Parties will clearly indicate on the request the reason for urgency and the date by which a response is required.

SAFETY CRISIS MANAGEMENT

In case of a safety crisis, e.g., where safety issues have a potential impact on the indication(s), on the conduct of the Study, may lead to labeling changes or regulatory actions that limit or restrict the way in which the Product is used, or where there is media involvement, the Party where the crisis originates will contact the other Party as soon as possible.

The Parties agree that Genentech/Roche shall have the final say and control over safety crisis management issues relating to the Product. *Sponsor* agrees that it shall not answer such queries from media and other sources relating to the Product but shall redirect such queries to Genentech/Roche

